**15.2.2. MISSING DATA METHODS FOR SECONDARY EFFICACY VARIABLE(S)**

All analyses of other secondary efficacy variables will be based on available data. No missing data will be imputed. For sensitivity analysis of ACR response, Missing ACR responses will be treated as non-responders.

**15.2.3. ANALYSIS OF SECONDARY EFFICACY VARIABLE(S)**

For all continuous efficacy variables including DAS28, each component of the ACR criteria, change from baseline of DAS28 will be summarized descriptively by treatment group and visit using n, mean, standard

Document:	\\ieedc-vnasc01\Biosdata\Archigen\SAIT101\YWA21301\Biostatistics\Documentation\SAP	
Author:	Version Number:	V2.0
	Version Date:	13Feb2019

Template No: CS_TP_BS016 Revision 4	Reference: CS_WI_BS005
Effective Date: 01Apr2016	

deviation, median, minimum, and maximum; and analyzed as main efficacy variable by using ANCOVA model with each baseline value as covariate.

Categorical efficacy variables, such as proportion of patients with ACR20/50/70 response, major clinical response, clinical remission and EULAR response will be summarized descriptively by treatment group and visit using counts and proportions; and the Wilson Score method will be used to calculate 95% CI. All summaries of secondary efficacy variables and comparison between SAIT101 and MabThera® will be based on FAS and PP. A logistic regression method (Reeve, 2016; [Appendix 5](#)) will be employed with baseline DAS28 as covariate. All efficacy variables will be listed.

To visualize results of efficacy variables, a line chart will be developed by treatment group and visit at Week 8, 16, 24, 36 and 52 for changes from baseline in DAS28-CRP based on FAS and PP; a bar chart will be created for ACR20/50/70 response by treatment groups and the visits based on FAS and PP. Besides, to evaluate impact of Mexican site 10703, the above two charts for site 10703 will be created.

#### 15.2.4. SUBGROUP ANALYSES

The main efficacy endpoint will be repeated on following subgroups as exploratory analyses based on the FAS and the PP.

- Region – EU, US, Others
- Age group – 18-60 years, >60 years
- Gender – Female, Male
- CRP at baseline – <10, ≥10
- ADA status at baseline – Positive, Negative
- TJC≥8 and SJC≥8 at baseline

Secondary endpoints of ACR20 at Week 24 and DAS28-ESR at Week 24 will be repeated as exploratory analysis based on the FAS and the PP.

#### 15.2.5. EXPLORATORY ANALYSES FOR COMPARISON BETWEEN SAIT101 AND RITUXAN, MABTHERA AND RITUXAN

All comparison for main and secondary efficacy variables between SAIT101 and MabThera® will be repeated for MabThera® and Rituxan® and SAIT101 and Rituxan® as exploratory analyses.

#### 15.2.6. IMPACT ANALYSIS FOR MEXICAN SITE 10703

An impact analysis will be performed to evaluate the impact of site 10703 on the main efficacy analysis. The impact analysis will entail adding two fixed effects to the primary model: Site10703 (Yes/No), Site10703 x Treatment interaction, and testing both effects at the two-sided 5% significance level.

## 16. Safety Outcomes

All outputs for safety outcomes will be based on the SAF.

There will be no statistical comparisons between the treatment groups for safety data.

---

Document:	\\eedc-vnasc01\Biosdata\Archigen\SAIT101\YWA21301\Biostatistics\Documentation\SAP		
Author:		Version Number:	V2.0
		Version Date:	13Feb2019
Template No:	CS_TP_BS016 Revision 4	Reference:	CS_WI_BS005
Effective Date:	01Apr2016		

## 16.1. ADVERSE EVENTS

AEs will be coded using MedDRA 19.0 or higher.

For an AE change from non-serious AE to be a serious AE, it will be treated as a continuous event and count for once only in AE summary.

A treatment-emergent AE (TEAE) will be defined as any AE with an onset date on or after the date of first dose of study drug. AEs with increased severity during the treatment period will be considered as TEAEs whether already present during the pre-treatment period or not. Pre-existing AEs before the treatment period with no increase in severity during the treatment period will not be considered as TEAEs.

See [Appendix 1](#) for handling of partial dates for AEs. In the case where it is not possible to define an AE as treatment emergent or not, the AE will be classified by the worst case; i.e. treatment emergent.

For AE table summary, patients will be counted at most once for each Preferred Term (PT) and each System Organ Class (SOC).

All AEs will be listed.

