### **3 STUDY DESIGN**

#### **3.1 Summary of Study Design**

This is a multicenter, randomized, double-blind, parallel group study to compare the PK, PD, safety, efficacy, tolerability, and immunogenicity of SAIT101 versus MabThera® versus Rituxan® in patients with RA. This study will take place globally across approximately 70 study centers in order to randomize approximately 282 patients. The study consists of Part A from baseline for PK and efficacy analysis, followed by Part B from Week 24 to 52 for safety follow-up that also collects transition data.

Patients with RA who have had an inadequate response to at least 3 months' treatment (according to the approved treatment and dosage) or intolerance (at Investigator's discretion and/or experience of severe adverse event [AE] or toxicity such as infusion related reaction, hypersensitivity, anaphylaxis or severe toxicity) to anti-TNF therapy. All the Screening assessments should be performed within 30 days prior to randomization on Day 1 (Visit 2, Baseline), except in patients who require prophylaxis of latent tuberculosis or a washout of current anti-TNF medication or other biologic and non-biologic DMARD treatment except MTX. For these patients the Screening period may be extended to allow for the washout required, but will not exceed 60 days. In these patients all Screening assessments must be performed within 30 days prior to randomization with the exception of the informed consent and chest X-ray (see Section 3.2.5).

In Part A, patients will be randomized in a 1:1:1 ratio to receive one course of SAIT101 (n=94) versus Rituxan® (n=94) versus MabThera® (n=94).

At Week 24, patients will be evaluated for a second course of the infusion.

In Part B, eligible patients in the SAIT101 arm will receive the second course of SAIT101 treatment at Weeks 24 and 26. Eligible patients in the MabThera® arm will receive the second course of MabThera® treatment at Week 24 and 26. Eligible patients in the Rituxan® arm will be randomized in a 1:1 ratio to receive SAIT101 or Rituxan® treatment at Weeks 24 and 26. Patients will be followed up for safety till Week 52.

[figure not shown]
For each course of infusion, patients will receive two infusions of 1,000 mg (10 mg/mL) SAIT101 or Rituxan® or MabThera® for i.v. infusion for the treatment.

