- t On Day 1, Day 15 (Week 2), and Week 24: immunogenicity sample will be collected before start of infusion. Wherever possible immunogenicity blood samples will be taken at the same time as blood is drawn for other analyses to limit repeated venipuncture. Immunogenicity sampling is also taken when patients show signs or symptoms of immune-response-related adverse events.

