## 5. General Considerations

All patients will be tabulated according to their initial treatment group for analyses when all study team are blinded; while for final analysis (W52 CSR), both initial first and second courses of study treatment group will be considered, regardless of any dose adjustment during study conduct.

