## 17. Immunogenicity Outcomes

The immunogenicity analyses and comparison will be performed using the SAF.

Document: \\ieedc-vnasc01\Biosdata\Archigen\SAIT101\YWA21301\Biostatistics\Documentation\SAP  
 Author: Version Number: V2.0  
 Version Date: 13Feb2019

Template No: CS\_TP\_BS016 Revision 4 Reference: CS\_WI\_BS005  
 Effective Date: 01Apr2016

The incidence of Human anti-chimeric antibodies (HACA) and neutralizing antibody at Day 1 predose and at Weeks 1, 2, 4, 12, 16, 24, 36 and 52 will be summarized by treatment group and visit.

- Incidence (%)= number of subject with specific assessment result/ number of subject with available assessment results \* 100%

Overall positive of HACA and neutralizing antibody from Day 1 will be summarized. Patients with at least one positive result up to Week 24, 52 after Day 1 will be considered as overall positive; Otherwise, patient without any positive result up to Week 24, 52 after Day 1 will be considered as overall negative.

For the treatment difference among treatment groups listed below, the proportion, 95% CI for the proportion, proportion difference, standard deviation, and 95% CI for the proportion difference will be reported. The Wilson Score method will be used to calculate 95% CI.

- Response:
  - HACA positive
  - HACA negative
  - Neutralizing antibody positive
  - Neutralizing antibody negative
- Treatment groups:
  - Rituxan®- Rituxan® (reference group)
  - Rituxan®- SAIT101
  - SAIT101-SAIT101
  - MabThera®-MabThera®

Listings for immunogenicity assessment data by subject will be provided.

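### The SAP text counts adverse events only from the first Part A dose, which dilutes the re-randomised Rituxan-to-SAIT101 versus Rituxan-to-Rituxan comparison

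*SAP*

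**What the plan says.** **Design.** Protocol 3.1 describes Part A "followed by Part B from Week 24 to 52 for safety follow-up that also collects transition data". Under SAP 2.4, eligible Rituxan patients are re-randomised 1:1 to SAIT101 or Rituxan at Week 24. SAP 2.6 merges Parts A and B into one final analysis.

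**Adverse events.** SAP 16.1 states that a treatment-emergent event "will be defined as any AE with an onset date on or after the date of first dose of study drug". For the summary tables, "patients will be counted at most once for each Preferred Term (PT) and each System Organ Class (SOC". No second window opens at the first Part B infusion. SAP 16 rules out statistical comparison of groups for safety.

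**Grouping.** SAP 5 says that for the final analysis "both initial first and second courses of study treatment group will be considered". SAP 16 does not itself name the columns of the adverse event tables. SAP 7 leaves their format and content to templates that are not among the documents.

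**Antibodies.** SAP 17 reports HACA and neutralizing antibody incidence "at Day 1 predose and at Weeks 1, 2, 4, 12, 16, 24, 36 and 52 will be summarized by treatment group and visit". It adds an overall result: "Patients with at least one positive result up to Week 24, 52 after Day 1 will be considered as overall positive". It then asks for proportions and proportion differences with 95% confidence intervals across four sequences, with Rituxan-Rituxan as reference. It does not say whether these use the by-visit or the overall result. The timing of the samples is in a footnote to Protocol Table 2: "On Day 1, Day 15 (Week 2), and Week 24: immunogenicity sample will be collected before start of infusion".

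**The concern.** Until Week 24 the Rituxan-SAIT101 and Rituxan-Rituxan groups have received the same product. Events in that period say nothing about switching. A table that runs from Day 1 to Week 52 adds them to both columns, so a real post-switch difference looks smaller.

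Once-per-term counting makes this sharper for recurring events. Protocol 5.4.5 has infusion reactions recorded under a single event term and says severe ones typically come with the first infusion. A patient who reacted in Part A and reacts again after switching adds nothing further to incidence. The severity table keeps only the worst grade, so a repeat of equal or lower grade is not visible there either.

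In a similarity trial, dilution pulls towards the conclusion the sponsor hopes for. Because no formal safety comparison is planned, the descriptive tables are the main safety readout on switching, and their time window matters.

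**Working it through.** **1. Plan figures.** The plan gives no sample size or power for the switch comparison. The nearest stated number is 94 randomised per group, which reproduces: 84 / 0.90 = 93.3, rounded up to 94. If every Rituxan patient were eligible, each re-randomised group would have at most 94 / 2 = 47.

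**2. How much of the window precedes the switch.** By time: 24 / 52 = 46%. By patients' first events, assuming a constant hazard and 52-week incidence P, the share is [1 − (1 − P)^(24/52)] / P. This gives 47% at P = 10%, 51% at P = 30% and 55% at P = 50%. Front-loaded events, such as infusion reactions, could be higher; the documents give no rates.

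**3. Size of the dilution.** Let pA be Part A incidence, the same in both groups in expectation because of re-randomisation. Let pB0 and pB1 be the Part B incidences for Rituxan-Rituxan and Rituxan-SAIT101, independent of Part A. Then:

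- cumulative incidence = 1 − (1 − pA)(1 − pB)
- cumulative difference = (1 − pA)(pB1 − pB0)

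Assumed rates pB0 = 5% and pB1 = 15%, a Part B difference of 10 points:

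| pA | Rituxan-Rituxan | Rituxan-SAIT101 | Difference shown |
|---|---|---|---|
| 20% | 1 − 0.80 × 0.95 = 24% | 1 − 0.80 × 0.85 = 32% | 8 points |
| 30% | 1 − 0.70 × 0.95 = 33.5% | 1 − 0.70 × 0.85 = 40.5% | 7 points |

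**4. Effect on precision.** No test is planned, so power serves here only as a gauge. Take 47 per group, assumed Part B incidence 10% versus 30%, and a two-sided 5% normal-approximation test of two proportions.

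- Part B events only: 10% versus 30%, difference 20 points, power 68%.
- From Day 1 with pA = 20%: 28% versus 44%, difference 16 points, power 36%.
- From Day 1 with pA = 10%: 19% versus 37%, difference 18 points, power 49%.

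The loss comes from both the smaller difference and the higher background rate.

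**5. Antibodies.** Scheduled samples after Day 1 fall at Weeks 1, 2, 4, 12, 16, 24, 36 and 52. The Week 24 sample is pre-infusion, so 6 of 8 (75%) precede the switch. The overall result is defined at both Week 24 and Week 52. Within a sequence, overall positive by Week 52 minus overall positive by Week 24 is the number newly positive afterwards. That works only if both cut-offs are shown in the same sequence columns. It yields a count, not a defined variable with its own denominator, difference and interval. A positive at Week 36 or 52 in the by-visit table may simply persist from Part A.

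**6. What the SAP already separates.** Laboratory values, vital signs and HACA/NAb are summarised by visit. CD19+ counts are summarised by study part, with plots covering Weeks 24 to 52 (SAP 14.1). B cell recovery is reported only after Week 24 (SAP 16.5). Adverse events have no equivalent split in the text.

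**The case against.** The strongest reply is that little depends on this. The switch has no hypothesis and no power, and Part B is described as safety follow-up. Every adverse event is listed, Protocol 6.6.1 puts start date and study day in the SAE and ADR listings, and each SAE has a narrative, so post-switch events can be identified. A worse repeat does appear in the severity table. Re-randomisation should balance Part A events between the two Rituxan-origin groups. Some patients with severe or repeated reactions in Part A are taken off study treatment and never reach the switch, so independence is only approximate. The table templates might contain a Part B table.

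All of that is fair, and it limits the point. A listing is not a summary, however. SAP 3.3 leaves undescribed exploratory analyses to ad hoc work after unblinding, so a Part B table produced then would not be prespecified.

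A reader might go further than the documents allow in four ways:

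- *The switch is judged mostly on pre-switch events.* Only 46% of follow-up is pre-switch. Under a constant hazard, first events pass one half only at a 52-week incidence of about 30% or more.
- *All safety and antibody results accumulate from Day 1.* The outputs in step 6 do not.
- *The comparison is biased by imbalance.* Between the two re-randomised groups it is dilution and noise. Comparisons with the other sequences lack that protection.
- *A threefold risk shrinks to 1.33* (15/5 against 32/24). The arithmetic is right, but the SAP reports percentages and, for antibodies, differences. On that scale the same example moves from 10 points to 8.

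**Conclusion.** The concern holds in a limited form. As written, the adverse event summaries have one window, opening at the first Part A dose, and once-per-term counting. If they are tabulated by sequence, the Rituxan-SAIT101 versus Rituxan-Rituxan difference shrinks by the factor (1 − pA), and a post-switch repeat of the same term adds nothing to incidence. With assumed rates the loss is 2 points of 10 at pA = 20% and 3 points of 10 at pA = 30%.

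For antibodies the gap is narrower: the counts are largely recoverable by subtraction, but the variable of interest and its interval are not defined.

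This rests on illustrative rates, independence of Part A and Part B events, sequence columns inferred from SAP 5, and the absence of any Part B table from the SAP text, since the templates could not be checked. No planned equivalence conclusion is affected. It is a worthwhile, inexpensive improvement.

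**What to change.** Before unblinding:

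- **SAP 16.1.** Add Part B-emergent summaries of TEAEs, SAEs, AESIs, infusion reactions and immune-response-related events. Count events with onset or worsening on or after the first Part B infusion. Use patients with at least one Part B infusion as the denominator and the four sequences as columns.
- **SAP 17.** Define HACA and neutralizing antibody newly positive after the Week 24 pre-dose sample, among second-course patients negative at every sample up to and including that one. Report the Rituxan-SAIT101 minus Rituxan-Rituxan difference with a 95% confidence interval. State whether the existing proportion differences use the by-visit or the overall result.
- Keep the cumulative Day 1 tables alongside. If the templates already contain a Part B table, refer to it in the SAP text.

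The cost is SAP wording and a few more tables, from event dates and samples already collected. The drawback is small groups, at most 47 in each re-randomised arm and fewer if eligibility is limited, so the results will be descriptive with wide intervals.

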### TEAEs

Incidence of TEAEs will be summarized by the number and percentage of patients experiencing events by SOC and PT.

### Severity

Severity is classified as mild/moderate/severe (increasing severity) per eCRF. A TEAE with a missing severity will be classified as missing. If a subject reports a TEAE more than once within that SOC/PT, the AE with the worst-case severity will be used in the corresponding severity summaries.

### Relationship to Study Drug (Causality)

The causal relationship between the study drug and the AE should be defined as unrelated or related. TEAEs with a missing relationship to study drug will be regarded as “related” to study drug. If a subject reports the same AE more than once within that SOC/ PT, the AE with the worst-case relationship to study medication will be used in the corresponding relationship summaries.

### TEAEs Leading to Discontinuation of Study Drug

TEAEs leading to permanent discontinuation of study drug are identified by choosing ‘Drug permanently withdrawn’ in the question ‘Action taken with study drug’ on the Adverse Events page of the eCRF, and will be summarized by SOC and PT.

### TEAEs Leading to Study Drug Interruption

TEAEs leading to study drug interruption are identified by choosing ‘Drug interrupted’ in the question ‘Action taken with study drug’ on the Adverse Events page of the eCRF, and will be summarized by SOC and PT.

### Serious Adverse Events

Serious adverse events (SAEs) are identified by choosing ‘Yes’ in the question ‘Is the adverse event serious’ on the Adverse Events page of the eCRF. A summary of serious TEAEs by SOC and PT will be prepared, and all SAEs will be listed.

### TEAEs Leading to Death

TEAEs leading to death are identified by choosing ‘Yes’ in the question ‘Resulted in death’ on the Adverse Events page of the eCRF. TEAEs leading to death will be summarized by SOC and PT, and listed.

---

Document:	\\ieedc-vnasc01\Biosdata\Archigen\SAIT101\YWA21301\Biostatistics\Documentation\SAP		
Author:		Version Number:	V2.0
		Version Date:	13Feb2019

Template No: CS\_TP\_BS016 Revision 4  
Effective Date: 01Apr2016

Reference: CS\_WI\_BS005

### TEAEs of Adverse Drug Reaction (TEADRs)

An adverse drug reaction (ADR) is identified by choosing 'Related' in the question 'Causal relationship to study drug' on the Adverse Events page of the eCRF. TEAEs with a missing relationship to study drug will be regarded as "related". TEADRs will be summarized by SOC and PT, and listed.

### TEAEs of Special Interest (AESI)

The incidence of TEAEs of special interest are identified by choosing 'Yes' in the question 'Is this event an AESI (Adverse Event of Special Interest)' on the Adverse Events page of the eCRF. TEAEs of special interest will be summarized by SOC and PT, and listed. Besides, TEAEs of special interest to infusion reactions will be summarized by SOC and PT.

### TEAEs Related to Immune-response

The incidence of TEAEs related to immune-response are identified by choosing 'Yes' in the question 'Is this AE 'immune-response-related' of the Adverse Events page of the eCRF. TEAEs related to immune-response will be summarized by SOC and PT, and listed.

## 16.2. LABORATORY EVALUATIONS

Results from the laboratory test will be included in the reporting of this study for hematology (including erythrocyte sedimentation rate), clinical chemistry (including C-reactive protein and rheumatoid factor), virology, and urinalysis parameters.

Presentations will use SI Units. Unit conversions will be performed by Data Management (DM) in the database where necessary.

Quantitative laboratory measurements reported as "< X", i.e. below the lower limit of quantification, or "> X", i.e. above the upper limit of quantification, will be converted to X for the purpose of quantitative summaries, but will be presented as recorded, i.e. as "< X" or "> X" in the listings.

The following summaries will be provided for laboratory data:

- Actual and change from baseline by visit (for quantitative measurements).
- Shift table of incidence of abnormal values (abnormal low, normal, abnormal high), based on normal range, from baseline to each post-baseline visit.
- Overall abnormalities incidence result will be summarized, and further break down by high/low abnormalities. Patients will be counted at most once for a high or low abnormality for each laboratory parameter.
- Overall abnormalities from Day 1: Patients with at least one abnormal (abnormal high or abnormal low) result up to Week 24, 52 after Day 1 will be considered as overall abnormal; Otherwise, patient without any abnormal result up to Week 24, 52 after Day 1 will be considered as overall normal.

Listing of all laboratory test values with the abnormal values flagged out with H (high) or L (low).

### Laboratory Normal Ranges

Quantitative laboratory measurements will be compared with the relevant laboratory normal ranges in SI units:

- Abnormal high: Upper than the laboratory reference range
- Normal: Within the laboratory reference range (upper and lower limit included).
- Abnormal low: Lower than the laboratory reference range

### Drug-Induced Liver Injury (DILI)

Drug-induced liver injury will be assessed through the number of possible Hy's law cases as following:

---

Document:	\\eedc-vnasc01\Biosdata\Archigen\SAIT101\YWA21301\Biostatistics\Documentation\SAP	Version Number:	V2.0
Author:		Version Date:	13Feb2019
Template No:	CS_TP_BS016 Revision 4	Reference:	CS_WI_BS005
Effective Date:	01Apr2016		

- ALT or AST > 3 × ULN, and
- ALP < 2 × ULN, and
- Total bilirubin ≥ 2 × ULN

All parameters above should be measured at the same visit. The possible Hy's law cases will be summarized and listed by treatment groups.

